11. ETHICS/PROTECTION OF STUDY PARTICIPANTS

11a. Informed Consent Process

Health facility participation: To ensure appropriate permissions and access at the facility level, we will engage with the Kenyan Ministry of Health, relevant county health management and facility administration teams prior to entering health facilities. Each facility designee will provide the study team with a list of potentially eligible HCWs to participate in the training. Facility managers will be asked separately to provide informed consent to complete an anonymous survey on facility characteristics at the start and end of the study.

HCW participants: All HCW participants will provide written consent prior to study activities. HCW participants will sign a standard written informed consent form describing the study procedures and risks. Consent forms will be IRB-approved, and the participant will be required to read and review the document or have the document read to him or her. HCWs will be informed that they have the option to decline signing the consent. They will be informed that unannounced patient actors will present to their facility during the study, but they will not be told the specific time or date of SP visits. Participants will be informed that they are free to withdraw their permission at any time during the study. A copy of the informed consent document will be given to participants for their records. In the unlikely event of an HCW participating in an unannounced patient actor interaction prior to consent, any data collected from the interaction will be destroyed.

Waiver to release SP training videos: HCWs will also have the opportunity to sign waivers to authorize use of SP encounter videos for educational purposes by the study team (e.g. dissemination activities, examples for future SP trainings, online courses, conference presentations). Waivers will be signed at the end of the training. Only videos where participants have signed waivers will be used for these purposes. Videos where a participant has not signed the waiver will not be used beyond the training.

Exclusion of women or minorities: There are no exclusions of women or minorities for the HCW participants. Eligibility is based on age, occupation and employment status at the study facilities.

11b. Participant Confidentiality

Study staff will take strict measures to maintain confidentiality for all participants. No names will be recorded on data collection forms. HCW participants will be assigned unique study identification (ID) numbers. Participants will be assigned a non-identifiable study code upon enrollment. Study analysts will receive only coded data. The links to participant identifiers will be retained in a password-protected file on an encrypted computer. Data collected will be kept confidential and access restricted to study staff. All video-recordings of the SP encounters will be kept in an encrypted cloud server. Video data are potentially identifiable. Only

videos of HCWs who have signed release waivers will be stored after the two-day training. All other data will be kept in password-protected databases, in a locked study office, accessible only to study personnel.

11c. Risks and Benefits

Physical risks: There are no medical interventions associated with the study, therefore we anticipate no risk of serious physical harm to participating HCWs.

Psychosocial or other risks: Other potential study risks to the HCW participants include breach of confidentiality, emotional distress associated with the sensitive nature of HIV counseling for AGYW, and stress associated with group critique/feedback of videotaped training encounters.

Procedures to minimize psychological risks: All participants will be assured that their participation is voluntary and that they may withdraw from the study at any time. Trained facilitators will oversee debriefing sessions with HCWs. For HCW training attendees, each clinical training intervention will begin with a session on professional standards, expectations, and confidentiality, building an atmosphere of peer-support and collaboration. All HCW participants will agree to not share individual performance information from the SP trainings outside of the learning group.

Procedures to minimize other risks: Study staff will be trained to take all precautions to ensure confidentiality of participation and data collected and will have standardized operating procedures for ensuring data security. Risk of breach of confidentiality of study data is low, as all HCW data collected will not include names and will be located on a password protected server and encrypted prior to upload. Study data is not very sensitive in nature and focuses on facility-level characteristics and provider experiences during SP encounters. Study staff will be trained in the importance of confidentiality during human participants training prior to study implementation. We will not share individual-level HCW data with health facilities in order to minimize risk of a negative reaction by an employer if they choose to participate or not participate in this study. In the event of reported social harm, we have developed standard operating procedures for referrals to local social agencies that will be incorporated into the HCW training.

Direct benefits: HCWs will receive direct and immediate benefit in receipt of SP training to improve their skills in delivery of adolescent friendly HIV services and counseling. HCWs in previous studies have specifically requested this training.

Indirect benefits: The study can identify important information regarding AGYW adherence of PrEP to guide the best model for PrEP delivery which will benefit individuals in Kenya and other African countries with high HIV prevalence.

12. DISSEMINATION AND IMPACT

12a. Community dissemination

Results of the SP mystery shoppers and training program pilot evaluations will be shared with community groups, key stakeholders, HCWs and clinic program leaders. The SP training scenarios, curriculum, and approach will also be shared with Ministry of Health for consideration as a strategy to improve PrEP service quality, provider communication and counseling at public sector facilities in Kenya.

12b. Anticipated impact from the study

This study will provide detailed analyses of PrEP services in the context of PrEP counseling for AGYW in Kenya. These data are critical to understand programmatic effectiveness of new efforts to improve HCW adherence to guidelines and communication regarding PrEP for AGYW. Our study of unannounced SPs and SP training will provide evidence to support new interventions to improve PrEP counseling practices for AGYW, by improving communication with AGYW in PrEP service delivery. The Kenya Ministry of Health and National AIDS Control Program prioritizes evidence-based strategies for HIV prevention, and throughout the

course of the study, results will be shared with the Ministry of Health as they become available to maximize translational impact.

STUDY SCHEDULE

ACTIVITY	Q1 2019	Q2 2019	Q3 2019	Q4 2019	Q1 2020	Q2 2020	Q3 2020	Q4 2020	Q1 2021	Q2 2021	Q3 2021	Q4 2021	Q1 2022	Q2 2022
Recruitment and selection of 24 health facility sites														
Facility and HCW consent														
Facility site evaluation survey														
Training of SP actors with case scripts														
Unannounced SP baseline assessment														
HCW SP training														
Unannounced SP assessment (post-training)														
Analysis and Dissemination														

REFERENCES

1. UNAIDS. On the Fast-Track to end AIDS by 2030: Focus on location and population. Geneva, Switzerland: 2015.
2. Joint United Nations Programme on HIV/AIDS (UNAIDS). Get on the Fast Track to HIV: The lifecycle approach to HIV 2016. Available from: <http://www.unaids.org/en/resources/documents/2016/get-on-the-fast-track>.

Appendix I. Budget Summary and Justification (Overall Study including RCT using SP actors)

Appendix II. Potential Adverse Events

Appendix III. Facility Manager Consent Form

Appendix IV. HCW Consent Form

Appendix V. Facility Survey

Appendix VI. Unannounced Standardized Patient (SP) Checklist

Appendix VII. SP Training Checklist

Appendix VIII. HCW Pre/Post Survey

Appendix IX. HCW Training Evaluation Surveys

Standardized Patient Encounters to Improve Counseling for Pre-Exposure Prophylaxis (PrEP) for HIV Prevention to Adolescent Girls and Young Women (AGYW) in Kenya (PrIYA-SP)

Grant Number: R01 HD094630
ClinicalTrials.gov Number: NCT03875950

Statistical Analysis Plan

September 2021

STUDY SUMMARY

Background: The incidence of HIV in adolescent girls and young women (AGYW) continues to rise despite promising innovation in female-controlled HIV prevention strategies. Pre-exposure prophylaxis (PrEP) is an effective HIV preventive intervention that can be female-controlled. PrEP effectiveness is threatened by low adherence. Improved health counseling may improve uptake of and adherence to PrEP. Standardized patient actors (SPs) can help health providers to improve communication and counseling skills.

Goal: To facilitate AGYW uptake of and adherence to PrEP through a SP clinical training program to improve HCW communication skills and delivery of PrEP counseling services.

RCT Aim: To evaluate the effectiveness of an SP training intervention to improve HCW quality of PrEP counseling, including communication and counseling skills and accuracy in conveying information per national PrEP guidelines .

Methods: We will conduct a baseline assessment of PrEP counseling practices using unannounced SP actors as 'mystery shopper' evaluators at 24 facilities in Western Kenya. We will then randomly assign 12 facilities to an SP training intervention and 12 facilities to the control arm which will continue standard of care. Outcomes will be assessed by SP mystery shoppers who visit both intervention and control facilities.

Population: HCWs who provide PrEP services in Western Kenya.

Outcomes: The primary outcome will be the difference in mean PrEP competency score percent between the intervention and standard of care facilities, which reflects quality of the PrEP counseling session, defined as adherence to NASCOP guidelines of PrEP counseling/delivery and use of non-judgmental interpersonal skills, and measured as a score on a SP checklist after unannounced visits. A secondary outcome among intervention training participants will be change in interpersonal skills mean score percent between the first and last session.

Timeframe: January 2019 to August 2020

STUDY OUTCOMES

The primary outcome of the trial will be quality of PrEP counseling, summarized by an SP checklist score at unannounced clinic visits that will assess communication (e.g. listening without interruption, encouraged questions) and adherence to national guidelines on PrEP counseling and delivery (e.g. risk assessment, counseling on key messages, correct medication recommended). The secondary outcome, assessed in intervention arm will be change in interpersonal skills mean score percent between the first and last session. Communications and interpersonal skills measures are adapted from the Kalamazoo Consensus Statement (31) and other published tools (32-34)

SAMPLE SIZE CONSIDERATIONS

Primary trial outcome: Given a fixed number of clusters (24 facilities), we estimated the minimum number of SP encounters required to detect a 20 percentage-point difference in PrEP counselor competency score between intervention and control arms. Because it is uncertain what baseline PrEP competency will be, we estimated sample sizes to detect a 10-percentage point difference between the intervention and control arm varying the baseline competency percent, shown in Table 2. Under these assumptions, if PrEP competency is 61% in the control arm using baseline data and standard deviation of 17.7%, we would need an estimated 112 to 120 total SP encounters (4 to 6 per site). We will plan to conduct 6 visits per site (120 total), which assumes we only have 20 facilities, to ensure we have adequate power. Higher baseline competency would require a larger sample size to detect the same difference. The expected upper limit of SP encounters is 400.

Table 1. Sample sizes of SP encounters to detect a 10-percentage point difference in competency at 80% power, correlation coefficient (k) of 0.15, $\alpha=0.05$ and 24 facilities

Control group competency %	Intervention group competency %	Minimum cluster per arm required	SP encounters per cluster	Total SP encounters
0.61	0.71	14	4	112
0.61	0.71	11	5	110
0.61	0.71	10	6	120
0.61	0.71	8	7	112
0.61	0.71	8	8	128
0.61	0.71	7	9	126
0.61	0.71	6	10	120
0.61	0.71	6	11	132
0.61	0.71	6	12	144

STATISTICAL ANALYSES AND DESCRIPTION OF MAIN TABLES

Cluster RCT of PriYA-SP intervention

Question: Does the SP training intervention improve *quality* of provider delivery of PrEP services?

Overview: The primary analysis will evaluate effectiveness of the SP clinical training intervention on provider counseling skills and adherence to national guidelines

Primary outcome: Provider competency score using the endline unannounced SP checklist, expressed as a mean %, at the individual level. Each provider will receive a total score (% correct) from the checklist, rescaled to be out of 100.

Computing the total score per provider:

- The unannounced SP checklist contains 12 questions on adherence to PrEP guidelines with binary (done/not done) response options and 7 items on communication quality with 4 scaled response options (strongly agree to strongly disagree). Higher total scores represent higher competency.
- Each binary response option will be assigned 1 for 'done' and 0 for 'not done' for a total possible sub-score of 12.
- Communication items number #4, and 6-10 will be scored 3=strongly agree, 2=agree, 1=disagree, 0=strongly disagree. Question #5 is reverse coded (it is a negative question) as 3=strongly disagree, 2=disagree, 1=agree, 0=strongly agree, for total possible sub-score of 21.
- Each domain score will be converted a percentage of points possible. Total scores will be computed by adding the converted percentages and dividing by 2 (the number of domains), so that each domain is weighted equally.

Exposure: 12 Facilities that received the SP training intervention compared to 12 facilities without the SP intervention.

Adjustment variables: Pre-specified facility size/level, any baseline factors that differ between arms at $p<0.05$ level in addition to the primary exposure (intervention v. control) and stratification variables.

Clustering: Individuals within facilities

Data sources: HCW surveys, Facility survey, unannounced SP actor checklists

Primary analysis of trial endpoints: Primary analysis will be intention-to-treat (ITT).

[figure not shown]
A CONSORT diagram will be used to show the number of facilities and HCWs by arm during the trial, numbers excluded, and reasons for exclusion (Figure 1).

- Descriptive statistics, including means, medians, and proportions of data from baseline surveys and SP checklists will be generated including facility size, staffing, HCW age, gender, PrEP training exposure, and years providing HIV prevention services (Table 5). Baseline unannounced SP checklist scores will be presented as mean %. These data will be presented by trial arm in Table 1 to determine whether randomization achieved balance by potential confounding factors. Chi square and ranksum tests will compare differences in categorical and continuous variables by arm. Variables that differ between arms at the $p<0.05$ will be included *a priori* in the regression model.
- An intention-to-treat (ITT) analysis will be used to evaluate whether the SP training intervention resulted in higher mean competency score % at intervention compared to control facilities. The primary outcome will be at the individual level, adjusted for relevant baseline characteristics by arm and baseline evaluation scores. Generalized linear models (GLMM) with a Gaussian distribution and identity link, will be used to the difference in mean score %s between the intervention and standard of care facilities, accounting for facility cluster as a random effect (Table 6). We will consider individual SP as another random effect.

- In sensitivity analyses, we will evaluate the intervention effect on individual components of PrEP competency and communication quality in separate GLMM regression models as well as differences in overall mean % scores between cases, where case is entered as a fixed effect (a covariate).

Data sources: HCW surveys, Facility Surveys, Unannounced SP checklists, Exit Surveys

Figure 1. PrIYA-SP CONSORT diagram

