8. STATISTICAL CONSIDERATIONS

8a. Sample Size and Power

Given a fixed number of clusters (24 facilities), we estimated the minimum number of SP encounters required to detect a 20 percentage-point difference in PrEP counselor competency score between intervention and control arms. Because it is uncertain what baseline PrEP competency would be, we estimated sample sizes to detect a 20-percentage point difference between the intervention and control arm varying the baseline competency percent, shown in Table 2 (following page). Under these assumptions, if PrEP competency is 20% in the control arm, we would need an estimated 192 total SP encounters (8 per site). Higher baseline competency would require a larger sample size to detect the same difference. Given this range, and logistical constraints of larger samples with this type of evaluation, the expected upper limit of SP encounters is 400.

Table 2. Sample sizes of SP encounters to detect a 20% difference in competency at 80% power, correlation coefficient (k) of 0.15, $\alpha=0.05$ and 24 facilities

Control group competency %	Intervention group competency %	Cluster per arm (fixed)	SP encounters per cluster	Total SP encounters
0.2	0.4	12	8	192
0.3	0.5	12	10	240
0.4	0.6	12	11	264
0.5	0.7	12	12	288
0.6	0.8	12	13	312
0.7	0.9	12	30	720

8b. Analysis Plan

A CONSORT diagram will be used to show the number of facilities and HCWs by arm during the trial, numbers excluded, and reasons for exclusion. Baseline characteristics of each facility by intervention arm will be presented as descriptive statistics to assess whether balance of these factors was achieved through randomization using t-tests and McNemar's exact tests for continuous and dichotomous variables.

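### SAP Table 1 is captioned with a correlation of 0.15, but its cluster numbers match an ICC near 0.02; k is undefined, so the power of 6 visits per site depends on an unstated ICC

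*SAP*

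**What the plan says.** The SAP's section on sample size takes a control mean of 61% and an SD of 17.7% from the baseline data. Its table is captioned "Table 1. Sample sizes of SP encounters to detect a 10-percentage point difference in competency at 80% power, correlation coefficient (k) of 0.15", with alpha 0.05 and 24 facilities. For 4 to 12 encounters per facility it prints minimum clusters per arm of 14, 11, 10, 8, 8, 7, 6, 6, 6.

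The plan drawn from the table is: "We will plan to conduct 6 visits per site (120 total), which assumes we only have 20 facilities, to ensure we have adequate power". The text just before gives a wider range: "we would need an estimated 112 to 120 total SP encounters (4 to 6 per site".

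The target difference is given twice, and differently. The paragraph opens with "we estimated the minimum number of SP encounters required to detect a 20 percentage-point difference" and continues with "we estimated sample sizes to detect a 10-percentage point difference between the intervention and control arm". The table uses 10 points.

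Protocol section 8a uses the same symbol and value: "Table 2. Sample sizes of SP encounters to detect a 20% difference in competency at 80% power, correlation coefficient (k) of 0.15". Neither document says what k is, names a sample-size formula or reports an ICC. The planned comparison is "12 Facilities that received the SP training intervention compared to 12 facilities without the SP intervention".

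**The concern.** In a cluster-randomised trial, a correlation coefficient in a sample-size caption is naturally read as the ICC. An ICC of 0.15 with 6 visits per facility gives a design effect of 1 + 5 × 0.15 = 1.75. The unclustered requirement is about 49 encounters per arm, so that design effect needs about 86 per arm. The table's row for 6 visits provides 10 × 6 = 60.

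The number of visits, and the assurance that losing four facilities would be tolerable, both rest on this table. If the caption and the column use different correlations, a reader cannot tell what power the trial was planned to have.

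**Working it through.** **Inputs** (SAP, sample-size section): difference 0.10; SD 0.177; power 80%; alpha 0.05, taken as two-sided; k = 0.15.

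**Unclustered size.** n = 2(1.96 + 0.8416)² × 0.177² / 0.10² = 2 × 7.849 × 0.03133 / 0.01 = 49.18 per arm.

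**Clusters per arm** for m visits and ICC ρ: c = 49.18 × [1 + (m − 1)ρ] / m, rounded up.

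| Visits m | Printed | ρ = 0.0225 | ρ = 0.15 | k as coefficient of variation |
|---|---|---|---|---|
| 4 | 14 | 13.12 → 14 | 17.83 → 18 | 28.77 → 29 |
| 5 | 11 | 10.72 → 11 | 15.74 → 16 | 26.31 → 27 |
| 6 | 10 | 9.12 → 10 | 14.34 → 15 | 24.67 → 25 |
| 7 | 8 | 7.97 → 8 | 13.35 → 14 | 23.50 → 24 |
| 8 | 8 | 7.12 → 8 | 12.60 → 13 | 22.62 → 23 |
| 9 | 7 | 6.45 → 7 | 12.02 → 13 | 21.94 → 22 |
| 10 | 6 | 5.91 → 6 | 11.56 → 12 | 21.39 → 22 |
| 11 | 6 | 5.48 → 6 | 11.18 → 12 | 20.94 → 21 |
| 12 | 6 | 5.11 → 6 | 10.86 → 11 | 20.57 → 21 |

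The last column is the Hayes-Bennett formula with 17.7% as the within-facility SD: c = 1 + 7.849 × [2 × 0.177²/m + 0.15²(0.61² + 0.71²)] / 0.10².

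- ρ = 0.15 matches 0 of 9 rows. One-sided alpha does not help: 15, 13, 12, 11, 10, 10, 10, 9, 9.
- The coefficient of variation matches 0 of 9 rows.
- ρ = 0.0225 matches 9 of 9. Under this formula any ρ from about 0.0201 to 0.0231 does so.
- No clustering plus one extra cluster per arm, 1 + 49.18/m, matches 8 of 9. At m = 7 it gives 8.03, hence 9 against the printed 8. With an SD of 17.65 to 17.66, which rounds to 17.7, it matches all nine.

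**Protocol Table 2.** The Hayes-Bennett formula for proportions with k = 0.15 and 12 clusters per arm gives 7.76, 9.50, 10.82, 11.67, 11.92 and 11.19 visits, which round up to 8, 10, 11, 12, 12, 12. The protocol prints 8, 10, 11, 12, 13, 30. The first four rows fit a coefficient of variation and the last two do not, so the protocol does not settle what k means in the SAP.

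**Power of the plan.** With 6 visits and c facilities per arm, SE = √(2 × 0.177² × [1 + 5ρ] / (6c)). Power is Φ(0.10/SE − 1.96); the t figures use 18 or 22 degrees of freedom.

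| Assumed ICC | 20 facilities, normal (t) | 24 facilities, normal (t) |
|---|---|---|
| 0 | 87% (83%) | 92% (90%) |
| 0.0225 | 83% (79%) | 90% (87%) |
| 0.05 | 79% (74%) | 86% (83%) |
| 0.15 | 65% (60%) | 73% (69%) |

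At ρ = 0.15 the SE is 0.0427 (20 facilities) or 0.0390 (24). The difference detectable at 80% power is 2.8016 × SE, or 12.0 and 10.9 points.

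Power stays at 80% or more while 49.18(1 + 5ρ)/6 ≤ c. That is ρ ≤ (60/49.18 − 1)/5 = 0.044 for 20 facilities and ρ ≤ (72/49.18 − 1)/5 = 0.093 for 24.

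**The case against.** The strongest reply is that the table does follow from 0.15 once k is squared. If k is the between-facility SD as a fraction of the stated SD, then k² = 0.0225 is the ICC. All nine rows then come out with no adjustment, and the planning sentence agrees with its table: 83.5% power with 20 facilities and 89.5% with 24. No row of the SAP table uses an ICC of 0.15, and neither document reports an ICC large enough to bring power below 80%. Twenty facilities is also the cautious case, since 24 are planned.

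Most of this stands. A reader might infer that the table is simply wrong, or that the trial is underpowered at 65%. The documents support neither inference: the column has a coherent basis at an ICC near 0.02, and the 65% and 73% hold only if the ICC really is 0.15.

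It does not remove the discrepancy. Squaring k is inferred from the fit and stated nowhere. It is not the only fit, and it does not carry over to the protocol's table. If it was what was done, the caption gives as the correlation a number nearly seven times the ICC applied (0.15/0.0225 = 6.7). The margin is also thin: with a t reference, power at ICC 0.0225 and 20 facilities is 79%.

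A second reply is that the analysis is more precise than the table allows: "The primary outcome will be at the individual level, adjusted for relevant baseline characteristics by arm and baseline evaluation scores". This could recover part of a shortfall. At ICC 0.15, assuming a facility-level correlation of 0.5 to 1.0 between baseline and endline and the 2 to 3 baseline visits of protocol section 6c, the variance explained is 3% to 18%. Power is then 66% to 73% (20 facilities) or 74% to 81% (24). The table claims no such allowance.

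**Conclusion.** The concern holds in a limited form. The caption's correlation of 0.15, read as labelled, does not give the printed cluster numbers in any row. They correspond to an ICC of about 0.02, or to no clustering plus one extra cluster per arm, and the documents do not say which was used.

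The statement that 6 visits suffice with 20 facilities is therefore conditional. By the normal approximation it holds up to an ICC of about 0.044, and with all 24 facilities up to about 0.093. It fails at the 0.15 that the caption appears to state. These figures assume a two-sided alpha, equal visits per facility, an SD of 17.7% and no gain from baseline adjustment.

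It would go too far to say that the planned power has no basis, because the true ICC is unreported and a small one would support the plan. The defect lies in the reported justification. It does not bias the treatment estimate or change the type I error. It should be fixed, but it does not threaten the validity of the trial.

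**What to change.** In the SAP's sample-size section:

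1. Define k and name the formula.
2. State the ICC actually used and its source, for example an estimate from the baseline standardized-patient visits.
3. Make the caption and the column agree. If the ICC used was about 0.02, correct the caption. Only if 0.15 really is the ICC, replace the clusters-per-arm column with 18, 16, 15, 14, 13, 13, 12, 12, 11.
4. Restate power, or the detectable difference, for 20 × 6 = 120 and 24 × 6 = 144 visits over a range of ICCs such as the one shown above.
5. In the same paragraph, reconcile the 20-point and 10-point targets. Drop the option of 4 visits per site, whose row needs 2 × 14 = 28 facilities when 24 exist.

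The cost is a corrected caption or column and a few sentences. The stated power may become less favourable. No extra visits or data are needed to make this correction.

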5. APPENDICES

APPENDIX 1: DATA SOURCES

Data source	Description	Timing of data collection	Analysis purpose
Unannounced SP checklist	Standardized SP checklists to evaluate the HCW encounter with the SP actor at baseline and endline unannounced visits	Baseline and end of study	Primary outcome End of study scores will be compared between RCT arms; Baseline scores used as an adjustment variable
Facility Survey	Anonymous survey will be administered to a health facility manager at baseline to capture facility characteristics	Baseline	Assess adequacy of randomization; Provide data for potential adjustment of ITT analysis
HCW surveys	Pre/post surveys to assess knowledge of and self-rated competency in provision of PrEP to AGYW	Baseline and end of study	Assess change in knowledge/attitudes between baseline and end of study, all sites Compare end of study scores between trial arms
SP training checklist	Standardized SP checklists to evaluate quality of the simulated visit with HCWs in the intervention training	Immediately after each SP encounter among trial participants	Secondary outcome Change in mean competency % among intervention participants between the first and last session

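### Adding every baseline variable that differs between arms at p<0.05 lets chance imbalance choose the primary model's covariates and costs power; the short list the SAP already names is cheaper

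*SAP*

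**What the plan says.** In the SAP's analysis section, the adjustment-variables entry lists "Pre-specified facility size/level, any baseline factors that differ between arms at $p<0.05$ level", together with arm and the stratification variables. The primary-analysis bullets then give the screening method, "Chi square and ranksum tests will compare differences in categorical and continuous variables by arm", and the consequence: "Variables that differ between arms at the $p<0.05$ will be included *a priori* in the regression model". The candidates are in effect the rows of Table 5 in Appendix 2; the SAP sets no limit on their number.

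The same bullets describe the primary outcome analysis as "adjusted for relevant baseline characteristics by arm and baseline evaluation scores", and Appendix 1 confirms the second part: "Baseline scores used as an adjustment variable". The adjustment-variables entry, however, omits the baseline score. Table 6 has an unadjusted and a starred, adjusted β column and does not say which is primary.

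Protocol section 8b also plans adjustment for baseline characteristics and baseline scores, but it has no p<0.05 selection rule.

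**The concern.** The rule is written in advance and uses baseline data only, but the covariate set it produces is unknown until the randomized arms have been compared. Calling that set *a priori* is therefore not accurate. Under randomization the p-value measures how far chance has separated the arms on a variable. It carries no information on whether the variable predicts the competency score, which is the reason to adjust.

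In a large individually randomized trial this would cost little. Here the units are 24 facilities, or 20 if some are lost. A variable selected because it is associated with arm is collinear with the treatment term and uses a degree of freedom. Unless it predicts the score beyond the baseline score, it returns little. At stake are power and a primary estimate that depends on which Table 5 rows happen to cross 0.05.

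**Working it through.** **Inputs from the documents.** Effect 10 points, α=0.05 (taken as two-sided), 80% power, coefficient 0.15 and 6 visits per site come from the SAP's sample-size section. So do the mean and SD ("if PrEP competency is 61% in the control arm using baseline data and standard deviation of 17.7") and the fallback number of sites ("which assumes we only have 20 facilities"). Allocation is 12:12, stratified by facility size (protocol 5c). There are about 10 HCWs per site (protocol 5d) and 2–3 baseline encounters per clinic (protocol 6c).

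**Candidates, by count of Table 5.** There are 10 facility rows and 2 facility-mean attitude scores, so 12 facility-level rows. Five HCW rows (cadre counted once) make 17. The baseline score is excluded because it is already named.

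**Step 1: the SAP's own figure.** Per arm before clustering, n = 2(1.960+0.842)²×17.7²/10² = 49.2. Clusters per arm = n[1+(m−1)ρ]/m, rounded up. For m=6:
- ρ=0.15: 49.2×1.75/6 = 14.4, so 15. The SAP's table shows 10.
- ρ=0.0225 (0.15²): 49.2×1.1125/6 = 9.1, so 10. This value matches all nine rows of the table.

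Both values are carried below.

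**Step 2: how often chance selects something.** With 17 independent candidates at 5%, the expected number selected is 17×0.05 = 0.85, and P(at least one) = 1−0.95¹⁷ = 58%. The SAP does not say that the tests allow for clustering. If 5 HCW rows are tested ignoring it, with 10 HCWs per site and an assumed ICC of 0.15, the design effect is 1+9×0.15 = 2.35. The critical value 1.96 then acts as 1.96/√2.35 = 1.28, a false-positive rate of about 20%. P(at least one) becomes 1−0.95¹²×0.80⁵ ≈ 82%.

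**Step 3: cost of one selected facility-level variable.** By t-test approximation, r² = t²/(t²+df).
- 24 facilities: 2.074²/(2.074²+22) = 0.164; variance inflation 1/(1−0.164) = 1.20.
- 20 facilities: 2.101²/(2.101²+18) = 0.197; variance inflation 1.25.

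These are minimum values for a selected variable.

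**Step 4: power.** Simulation by regression on facility means, which is equivalent to the random-intercept model with equal visits and facility-level covariates. There were 4,000 runs per setting, with a t reference. The model always contained arm, a two-level size stratum and the baseline facility mean. Assumed: ICC 0.15, 3 baseline visits, baseline–endline facility correlation 0.9, independent non-prognostic candidates, and only facility-level rows screened. Twelve rows are 9 yes/no and 3 continuous; eight rows drop MCH, FP, CCC and Other. Paired figures are chi-square with / without continuity correction.

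| Facilities | Rows | Prevalence | Any flag, % | Power, short list, % | Power, rule, % | Loss, points |
|---|---|---|---|---|---|---|
| 24 | 12 | 0.5 | 31.1 / 53.3 | 74.0 | 69.2 / 66.2 | 4.8 / 7.8 |
| 24 | 12 | 0.85 | 20.9 / 35.9 | 74.0 | 71.4 / 69.4 | 2.6 / 4.6 |
| 24 | 8 | 0.5 | 23.7 / 38.5 | 73.6 | 69.5 / 67.9 | 4.1 / 5.7 |
| 24 | 8 | 0.85 | 17.8 / 26.6 | 73.6 | 70.7 / 69.4 | 2.9 / 4.2 |
| 20 | 12 | 0.5 | 22.3 / 42.1 | – | – | 4.2 / 7.1 |
| 20 | 12 | 0.85 | 17.2 / 29.1 | – | – | 2.4 / 4.3 |
| 20 | 8 | 0.5 | 20.0 / 30.0 | – | – | 3.4 / 4.8 |
| 20 | 8 | 0.85 | 16.2 / 22.9 | – | – | 2.4 / 3.4 |

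- An 8,000-run check of the mildest 24-facility case gave a loss of 2.1 points.
- At baseline–endline correlation 0.5, the 24-facility losses are 2.8 to 7.6 points.
- The loss falls on the flagged trials. With 12 rows, prevalence 0.5 and the correction, power there goes from 74.5% to 59.1% (24 facilities) and from 64.0% to 45.4% (20). Over all settings the drop is 12–17 points with 24 facilities and 14–19 with 20.
- If the 12 rows together explain half of the facility variance, power still goes from 73.9% to 69.3 / 66.1%.
- Type I error under the rule is 4.8–5.0%.
- With 17 facility-level candidates, 24 facilities and ICC 0.15, power goes from 73% to 64%; with 10, from 74% to 68%; with 5, from 73% to 70%.
- At ICC 0.0225, 12 rows take power from 85% to 77–80%.

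**Step 5: is any fixed list better?** No. Adding k non-prognostic facility covariates (k = 0, 1, 2, 3, 5) to the short list gives power of 73.2, 71.3, 68.6, 65.3 and 58.8% with 24 facilities (rule 68.4%), and 65.3, 61.9, 58.6, 55.8 and 47.8% with 20 (rule 60.8%). The rule is matched at about two extra covariates with 24 facilities, and between one and two with 20.

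**The case against.** The strongest objection is that the rule deals with realized imbalance, so average power is not the only measure. Take one continuous row that explains half of the facility variance (24 facilities, ICC 0.15). In the roughly 5% of trials where it is flagged, the short-list estimate is off by 3.1–3.9 points in the direction of the imbalance, and 95% interval coverage falls to 85–88%. The rule's estimate is off by about 0.1, with 95% coverage. The baseline facility mean does not absorb this: with 3 visits its reliability is 3×0.15/(1+2×0.15) = 0.35. This stands as a real trade-off. It does not reverse the conclusion, because average power in that same setting still favours the short list (73% against 68.5%), and a variable believed to be that prognostic can be named in advance.

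A second objection is that 0.15 as an ICC does not reproduce the SAP's table, so absolute power near 74% understates what the plan's own variance implies. That is correct for the level: at 0.0225 the short list has about 85% with 24 facilities, and in most settings the rule stays near or above 80%. The loss is nearly the same size under either reading.

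Third, the rule is mechanical, leaves no choice after outcomes are seen, and does not raise Type I error. All true, and the reason this is not a validity failure. The labelling gaps are housekeeping and add no weight.

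**Conclusion.** The concern holds. The SAP lets chance imbalance choose the extra covariates in the primary model, and the list it already names has higher average power whenever there are several candidates. The average loss is modest: 2–8 points with 24 facilities and 2–7 with 20 when only facility-level rows are screened. It is concentrated in the 16–53% of trials where a row is flagged. There is no false-positive inflation. The harm is lost precision and a primary model that is not fixed.

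The sizes rest on assumptions: the number, level, prevalence and independence of the candidates, the baseline–endline correlation, and two size strata. Treatment of the HCW rows matters most. Entered as facility means, which the SAP does not specify, they bring the total loss to 7–12 points with 24 facilities and 7–14 with 20. Entered per provider they add little: one mixed-model run gave 73.1% to 72.0%, which is weaker evidence than the table. With a single, strongly prognostic candidate and no others, the rule neither gains nor loses (73% both ways). The change is recommended rather than essential.

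**What to change.** 1. Delete the p<0.05 clause from the adjustment-variables entry and from the primary-analysis bullets.
2. Fix the primary model as arm, facility size/level and the stratification variable(s), and the baseline SP score, with facility as a random effect. Add the baseline score to the adjustment-variables entry.
3. State the form of the baseline score. The facility mean is workable: Table 5 already uses it, and with 2–3 baseline encounters among about 10 HCWs per site most endline providers have no baseline score of their own.
4. Label the starred β in Table 6 as the primary estimate and reword its footnote to match.
5. Keep Table 5 descriptive. Move adjustment for imbalanced variables to a labelled sensitivity analysis.
6. Name any further covariate only if it is expected to predict the score, and keep the list short (Step 5).

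The sentence "We will consider individual SP as another random effect" is a separate matter and can stay as it is for this edit.

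Cost: SAP wording only, as a dated amendment made before endline scores are compared by arm. The covariates are already collected, and the sample-size section shows that baseline scores were in hand. The price is the one described under the objection: a chance imbalance in an unlisted prognostic variable would be handled only in the sensitivity analysis. The SAP should also say whether size/level is one variable or two. A separate, non-prognostic level term costs about 2 points of power with 24 facilities (73.2% to 71.3%) and 3 with 20 (65.3% to 61.9%), with or without this change.
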